6. GENERAL ANALYSIS DEFINITIONS

6.1 TREATMENTS

There will be 4 basic treatment phases in this trial: screening, study treatment phase (with either empagliflozin 10mg or matching placebo), post-treatment and post-study. However, during the study treatment phase, patients are allowed to go off-treatment and subsequently re-start treatment. This may happen not at all or repeatedly for a given patient.

The purpose of the definitions below is to describe all the different study/treatment intervals, in which a patient can lie during the course of the trial. Note that the term "treatment regimen" also covers the "off-treatment" time periods.

Table 6.1: 1 Treatment regimens / study intervals

Label	Interval	Start date
Screening	Screening	Date of informed consent
Placebo/ Empagliflozin 10mg	Treatment	Date of first administration of double-blind study treatment
Off-treatment (if applicable)	During Treatment interval, but not on treatment	Date of last administration of the study medication before temporarily discontinuation + 1 day
Placebo/ Empagliflozin 10mg (if applicable)	During Treatment interval, after restart of study medication	Date study medication re-started
Post-treatment	Post-treatment	Date of last administration of study drug + 1 day
Post-study	Post-study	Date of trial completion +1 day

Details on the definition of on-treatment period for different endpoints are listed in [Table 6.1:2](#). The efficacy analyses will follow the intention-to-treat (ITT) principle in assigning patients to treatment groups, i.e. patients will be analysed as randomised.

Safety analyses will also assign patients to the treatment group as randomized.

If a patient erroneously receives the wrong trial drug, all subsequent medication packs dispensed to the patient will still be for the treatment group to which the patient was randomized. Therefore the adverse events will be analyzed as per randomized treatment, which is expected to reflect the prevailing treatment.

In the exceptional case that a patient took the wrong treatment, adverse events may occur while being on the wrong treatment. Analyses of this data are described in [Section 7.8.1.6](#).

Table 6.1: 2 Endpoint specific assignment to the on-treatment phase

Endpoint	Last day of assignment to the on-treatment phase (days after last intake of study medication)
Adverse events	7
Safety laboratory measurements, including Urine Albumin Creatinine Ratio (UACR)	3
Heart rate	1
Glycosylated haemoglobin (HbA _{1c})	7
FG	1
Body weight	1
Creatinine and estimated glomerular filtration rate (eGFR)	1
N-terminal pro B-type natriuretic peptide (NT pro-BNP)	1
Blood pressure	1
Patient reported outcome	7

6.2 IMPORTANT PROTOCOL DEVIATIONS (IPDS)

A protocol deviation (PD) is important, if it affects the rights or safety of the study patients or if it can potentially influence the primary outcome measures for the respective patients in a way that is neither negligible nor in accordance with the study objectives.

The IPDs will be described in the clinical trial report (CTR). A listing of patients with medication code broken will be provided.

Table 6.2: 1 Important protocol deviations

Category / Code	Description	Requirements	Excluded from
A	Entrance criteria not met		
A1	Target indication not met		
	A1.06 No chronic HF or no NYHA class II-IV	Inclusion criterion #3 not met	None
	A1.07 Conditions on ejection fraction (EF) not met	Inclusion criterion #4 not met	None
	A1.08 Conditions on NT-proBNP not met	Inclusion criterion #5 not met	None
	A1.09 Conditions on HF not met	Inclusion criterion #6 not met	None
A2	Inclusion criteria not met		
	A2.02 Age out of range	Inclusion criterion #1 not met	None

Table 6.2: 1 Important protocol deviations (cont.)

Category / Code	Description	Requirements	Excluded from
A2.08	Specific inclusion criterion for women of child-bearing potential not met	Inclusion criterion #2 not met	None
A3	Exclusion criteria met		
A3.44	Patient with unstable conditions	Exclusion criteria #1, #2, #7, #11 or #16 met	None
A3.42	Recently implanted ICD	Exclusion criterion #3 met	None
A3.43	Implanted CRT	Exclusion criterion #4 met	None
A3.29	Patients with cardiomyopathies as defined in the protocol	Exclusion criterion #5 met	None
A3.30	Any severe (obstructive or regurgitant) valvular heart disease, obstructive or regurgitant, or any valvular disease expected to lead to surgery during the trial in the opinion of the investigator	Exclusion criterion #6 met	None
A3.31	Atrial fibrillation or atrial flutter with a resting heart rate >110bpm	Exclusion criterion #8 met	None
A3.33	Systolic blood pressure at visit 1 or 2 out of range	Exclusion criterion #9. #10 met	None
A3.06	Indication of liver disease	Exclusion criterion #12 met	None
A3.09	Renal insufficiency or renal impairment (assessed by eGFR)	Exclusion criterion #13 met	None
A3.34	Haemoglobin at visit 1 below cut-off	Exclusion criterion #14 met	None
A3.35	History of Ketoacidosis	Exclusion criterion #15 met	None
A3.36	Gastrointestinal (GI) surgery or GI disorder that could interfere with study medication absorption in the investigator's opinion	Exclusion criterion #17 met	None
A3.37	Documented or active malignancy	Exclusion criterion #18 met	None
A3.38	Life expectancy of <1 years in the opinion of the investigator	Exclusion criterion #19 met	None
A3.39	Intake of restricted medications or any drug considered likely to interfere with the safe conduct of the trial	Exclusion criterion #20 met	None
A3.40	Treatment with any SGLT-2 inhibitor or SGLT-1 and 2 inhibitor	Exclusion criterion #21 met	None
A3.11	Intake of an investigational drug in another trial within 30 days prior to intake of study medication in this trial	Exclusion criterion #22 met	None
A3.41	Known allergy or hypersensitivity to empagliflozin	Exclusion criterion #23 met	None
A3.13	Relevant alcohol or drug abuse and condition affected study compliance	Exclusion criterion #24 met	None
A3.12	Specific exclusion criterion for premenopausal women not met	Exclusion criterion #25 met	None
A3.14	Any other clinical condition unsafe for participation	Exclusion criterion #26 met	None
B	Informed consent		
B1	Informed consent not available/not done	Informed consent date missing or inclusion criterion #9 not met	All
B2	Informed consent too late	Informed consent date was after Visit 1	None

Table 6.2: 1 Important protocol deviations (cont.)

Category / Code	Description	Requirements	Excluded from	
C	Trial medication and randomisation			
	C1.02	Incorrect trial medication taken	Wrong medication taken for more than 20% of the overall treatment duration Can only be finally judged after data base lock (DBL) since unblinding information is required.	None
D	Concomitant medication			
	D2.02	Use of prohibited medication	Use of SGLT-2 or combined SGLT-1 and 2 inhibitors after randomization but before EOT visit occurring at study close out.	None

6.3 SUBJECT SETS ANALYSED

The following patient sets are defined

- *Screened Set (SCR)*
Consists of all patients screened for the trial, with informed consent given and who completed at least one screening procedure at Visit 1.
- *Randomised set (RS)*
This patient set includes all randomised patients, whether treated or not.
- *Treated set (TS)*
This patient set includes all patients who were dispensed study medication and were documented to have taken at least one dose of investigational treatment.
- *Treated Set-Follow-up (TS-FU)*
All patients in the TS, for whom a follow-up visit was performed (i.e. values of planned assessments- KCCQ, EQ-5D, vital signs or lab data reported) between 23 and 45 days after last intake of study medication.

The TS-FU does not include patients, where no planned measurements were taken, which may happen in case of telephone FU visits. Patients with intake of open label SGLT-2 inhibitor between their EOT and FU visit are also excluded from the TS-FU set.

- *Pharmacokinetic Set (PKS)*
This patient set includes all evaluable patients of the treated set who provide at least one observation for at least one further PK endpoint of $C_{pre,ss,N}$ for empagliflozin.

6.4 SUBGROUPS

Subgroups to be considered in the analyses are provided below in [Table 6.4: 1](#). Missing categories for subgroup variables will not be considered in the respective analysis.

If there is missing information for any of the subgroups, where data is also collected in the IRT system, then the information as transferred from IRT will be used to assign a patient to a certain category.

Although several subgroup analyses are prespecified in [Table 6.4: 1](#), the subgroup analysis by Diabetes at baseline (diabetic, non-diabetic) is the medically and academically most important subgroup analysis.

Table 6.4: 1 Categories of covariates for displays of baseline characteristics and subgroup analyses

Variable	Categorization	Demo-graphics ¹	Subgroups for Efficacy endpoints ²	Safety ³
Diabetes at baseline	diabetic, non-diabetic	X	X	X (except ketoacidosis and hypoglycaemia)
	non-diabetic (Pre-diabetes, normal (no pre-diabetes)), diabetic (type 2 diabetes, type 1 diabetes)	X		X (Ketoacidosis and hypoglycaemia)
Age (years)	<50 50 to <65 65 to <75 75 to <85 ≥ 85	X		X
	< 70 ≥70	X	X	
Sex	male female	X	X	X
Region	NA, LA, Europe, Asia, Other ⁺	X		X (overall ⁴ only)
Ethnicity	Hispanic/ Latino Not Hispanic/ Latino	X		X (overall ⁴ only)
Race ^s	White Black/ African-American Asian Other including mixed race	X	X	X
BMI (kg/m ²)	<30 ≥30	X	X	
eGFR at baseline	≥90 60 to <90 45 to <60 30 to <45 20 to <30 <20	X		
	≥90 60 to <90 45 to <60 30 to <45 <30	X		X
	≥60 <60	X	X	

Table 6.4: 1 Categories of covariates for displays of baseline characteristics and subgroup analyses (cont.)

Variable	Categorization	Demo- graphics ¹	Subgroups for Efficacy endpoints ²	Safety ³
UACR	UACR (in mg/g): <30 >=30 to <=300 >300	X		
Baseline SBP	< / >= median		X	
Baseline BP	SBP<140 and DBP<90 vs. SBP>= 140 or DBP>=90	X		X (volume depletion AEs and hypotension AEs)
History of Atrial Fibrillation or Atrial Flutter ^{SS}	Yes/ No	X	X	
Baseline LVEF	</>=50	X		
	<50, 50 to <60, >=60	X	X	
History of HHF (in the last 12 months)	Yes / No	X	X	
Time since diagnosis of HF	<= 1 year, 1-5 years, > 5 - 10 years, >10 years	X		
NYHA at baseline	I/II/III/IV	X		
	II vs. III/IV		X	
NT-proBNP	< / >= median (calculated separately for patients with/without history of atrial fibrillation or atrial flutter ^{SS})		X	
Baseline uric acid	Tertiles (calculated separately for males and females)	X	X	
Baseline use of ACE- inhibitor, ARB or ARNi	Yes / No	X#	X	X (renal AEs, volume depletion AEs and hypotension AEs)
Baseline use of MRA	Yes / No	X#	X	

Table 6.4: 1 Categories of covariates for displays of baseline characteristics and subgroup analyses (cont.)

Variable	Categorization	Demo-graphics ¹	Subgroups for Efficacy endpoints ²	Safety ³
Baseline use of diuretics	Yes / No	X#		X (renal AEs, volume depletion AEs and hypotension AEs)
Baseline use of loop or high-ceiling diuretics	Yes / No	X#		X (renal AEs, volume depletion AEs and hypotension AEs)

¹ The column demographics shows categories shown in the overall demographics.

Demographics are not planned by subgroup.

² Subgroups planned for the primary endpoint, time to cardiovascular (CV) death, time to first HHF, HHF (first and recurrent), renal slope.

³ X means subgroups planned for overall AE summaries, AEs by SOC and PT, SAEs, AEs leading to discontinuation, decreased renal function, UTI, genital infection, volume depletion, hypotension and bone fracture.

⁴ Overall means overall AE summaries, AEs by SOC and PT, SAEs and AEs leading to discontinuation

⁵ Median calculated separately for baseline atrial fibrillation or atrial flutter (determined by ECG) / no baseline atrial fibrillation and atrial flutter (determined by ECG)

⁺ Region categorization: see [Table 9.1.1](#).

[#] part of the presentation of baseline concomitant therapy as outlined in [Section 7.2](#)

[§] Due to low number of patients in certain race categories, estimates for race subgroups may be unstable.

^{§§} history of atrial fibrillation or atrial flutter means atrial fibrillation or atrial flutter reported in any ECG before treatment intake or history of atrial fibrillation or atrial flutter reported as medical history.

Additional subgroup analyses for specific further endpoints are defined in [Section 7.6](#)

6.5 POOLING OF CENTRES

This section is not applicable because centre/country is not included in the statistical model.

6.6 HANDLING OF MISSING DATA AND OUTLIERS

6.6.1 Imputation methods

There will be no imputation of data for safety analyses. For patients who discontinue the trial treatment prematurely, all efforts will be made to follow patients for survival and for any other endpoints including the primary and key secondary endpoints until the end of the trial.

There will be different methods of looking at continuous longitudinal data.

Observed case on-treatment (OC-OT):

Only the available data that were observed while patients were on study medication (defined as time from first drug intake until last permanent treatment stop date plus the endpoint specific follow-up time (as defined in [Table 6.1:2](#)) are considered.

Measurements are assigned to planned weeks according to [Table 6.7: 1](#)

Observed case including data after treatment discontinuation (OC-AD):

All available data are considered, including values obtained on treatment or post-treatment.

Measurements are assigned to planned weeks according to [Table 6.7: 1](#).

As described in [Section 4](#), for patients that completed the treatment phase as planned (primary reason for end of treatment being completion of treatment period according to protocol), measurements after last study drug intake should not be considered. Therefore for those patients, any data after the endpoint specific follow-up time (as defined in [Table 6.1:2](#)) will not be included in the OC-AD analysis.

KCCQ imputation

If not otherwise noted, for endpoints of KCCQ scores, for patients who die, a worst score (score of 0) will be imputed for the score at all subsequent scheduled visits after the date of death where the score would have been assessed.

Multiple imputations:

A multiple imputations approach will be considered to impute missing data. Multiple imputation approaches taken are further specified in [Section 7](#) with the planned sensitivity analyses.

Imputation of missing covariates in multivariate Cox regression models and for recurrent event analyses

To avoid excluding patients from Cox regression analyses due to missing covariates, the overall population median of the corresponding variable will be imputed for continuous covariates and the most frequent category will be imputed for categorical covariates.

No imputation will be done for covariates included in treatment by subgroup interaction terms.

6.6.2 Missing data

Adverse event data

Missing or partial date information for AEs will be replaced according to general Boehringer Ingelheim (BI) rules described in the BI guidance for handling of missing and incomplete AE dates (2).

Partial onset dates from clinical event committee (CEC):

In the unlikely case that only the year is documented, the day and month will be imputed as 01 Jan unless the subsequently derived date is before randomisation; in this case the date of randomisation will be used as start date.

If year and month is present the day will be imputed as first of the month unless the subsequently derived date is before randomisation; in this case the date of randomisation will be used.

Death date

For patients with a record of death captured on the electronic case report form (eCRF) with missing or only partial death date from all available sources, the death date will be derived as the latest date of any dates as of: event onset and end dates from either the AE page, or CEC adjudicated onset dates, by using also imputed AE dates, last day known to be alive + 1 day, range of possible days based on partial death date and date of trial completion.

Missing information on the date of first administration of trial drug

If the date of first drug administration is missing but the patient was randomised, the date of the first drug administration will be set to the date of randomisation. If the date of first administration is partially missing with the month and year present, the day will be set to the date of randomisation if randomisation was in the same month. If randomisation was in the month prior to the first drug administration the missing day will be imputed as the first day of the month.

Missing date of trial completion (=last contact or date of death)

If the date is completely missing the following rules will be applied:

- If a patient has withdrawn informed consent, this date will be imputed by the date of IC withdrawal.
- If a patient died and has not withdrawn consent and is not lost to follow-up, this date will be imputed by the date of death.
- If a patient did not die, the date of trial completion will be imputed by the last date the patient was known to free of non-fatal events. This is defined as the maximum of
 - the last date the patient could be followed up for all non-fatal events as documented in the eCRF
 - last onset or end date of an AE
 - Onset of an adjudicated event
 - End of treatment
 - last visit date (NYHA class, EQ-5D, KCCQ, pregnancy test, vital signs, ECG, or central laboratory reported)

In case of a partially missing date, if the imputed date is before the first day (after the last day) of the month/year given as partial date, the first day (last day) of the month/year will be used.

All other cases need to be assessed by the trial team on an individual patient basis, using the above points as guidance.

Missing information on the date of trial medication stop

If the date is partially or completely missing, use the minimum of the following dates:

- End of treatment visit date if available
- Date of death
- Trial completion (last contact date)
- Longest extrapolated treatment duration (assuming 1 tablet/day)
- (in case for partially missing date) Last day of the year/month given as partial date

In case of a partially missing date, if the imputed date is before the first day of the month/year given as partial date, the first day of the month/year will be used.

All other cases need to be assessed by the trial team on an individual patient basis, using the points above as guidance.

Missing information on concomitant therapy dates

For incomplete date information generally the midpoint of the possible interval will be used. If only the year is present the day and month will be imputed as 01 July, if year and month is present the day will be imputed as 15. If the year is missing, the date will be considered missing.

If this leads to contradictions for the start or end date of a concomitant therapy (e.g. imputed end date before documented start date) a partial end date will be imputed as the end of the interval or a partial start date will be imputed as the start of the interval in the database to resolve this contradiction.

If the medication is reported as being taken at visit 2 (baseline) and the imputed start/end date contradicts this then the start/end date is imputed to the earliest/latest date respectively if this can resolve the contradiction.

Similarly if the medication is reported as not taken at visit 2 (baseline) and the imputed start/end date contradicts this then the start/end date is imputed to the baseline date/ 1 day prior to baseline respectively if this can resolve the contradiction.

All other cases or conflicting cases resulting from these imputation rules need to be assessed by the trial team on an individual patient basis.

Missing measurement to confirm “sustained” decrease

An eGFR (CDK-EPI)_{cr} reduction is considered sustained, if it is determined by two or more consecutive post-baseline central laboratory measurements separated by at least 30 days (first to last of the consecutive eGFR values). If there is no additional measurement \geq 30 days after the eGFR reduction is observed and the patient dies within 60 days of this measurement, then the eGFR reduction is also considered sustained.

Pharmacokinetic (PK) variables

Missing data and outliers of PK data are handled according to [\(3\)](#)

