14	Week 124	869	786	953
16	Week 148	1037	954	1121
18	...			
FU	FU	Trt stop + 30 days	Trt stop + 23 days	Trt stop + 45 days
KCCQ				
2	Baseline ^A	1	NA	1
4	Week 12	85	2	154
6	Week 32	225	155	295
8	Week 52	365	296	435
EOT	EOT / Post week 52	NA	436	Trt stop
FU	FU	Trt stop + 30 days	Trt stop + 23 days	Trt stop + 45 days

^A Only values taken prior to the start of treatment with randomised study drug can be considered baseline values. Time windows will be used for assignment of measurements to scheduled visits.

For examinations that are not planned at every on-treatment visit, the time windows will be defined according to the same algorithm, based on the midpoint between the planned visit day of such an examination. Examples for eGFR and KCCQ can be found in [Table 6.7: 1](#)

Only one observation per time window will be selected for analysis at an on-treatment visit – the non-missing value will be selected which is closest to the protocol planned visit day. If there are two observations which have the same difference in days to the planned day or if there are two observations on the same day, the first value will be used.

Baseline definition for concomitant therapies

Concomitant medication taken at baseline is any medication with start date ‘continued’ or before date of first study medication intake (randomisation date will be used for patients not treated) and end date continued on or after date of first study medication intake (randomisation date will be used for patients not treated).

Time windows for assignment of planned off-treatment measurement

For evaluation of the off-treatment assessment ‘at 30 day follow-up’ only values obtained at ≥ 23 days to ≤ 45 days after last trial drug stop will be considered.

The value that is closest to the planned day of 30 days after last trial drug stop will be used. If there are 2 values equally close, the later value will be used.

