6.8.2 Date of event

For adjudicated events, the date determined by the adjudication committee will be used; this can be different from the investigator reported date.

For the endpoints of time to CV death, time to all-cause mortality and time to non CV death the respective death date will be used rather than time to the first onset of the fatal AE.

For composite outcomes, e.g. time to adjudicated HHF or adjudicated CV death, the earliest onset date of the corresponding components will be used. For the component of CV death or other death components, date of death will always be used rather than the onset date also for composite outcomes.

For endpoints, where myocardial infarction (MI) and stroke are included as a fatal and non-fatal component, the onset of the event is considered for the derivation of time to first occurrence, not the date of death. For time to CV death the date of death is used for a fatal MI or fatal stroke.

The time to first occurrence type of endpoints based on laboratory data including endpoints including the requirement a “sustained” measurement are determined by the date of the first measurement that fulfils this condition.

For events with multiple possible episodes, such as HHF or all-cause hospitalisation, the onset date of the first episode will be used unless noted otherwise. The same applies to time-to-AE analysis.

For efficacy endpoint analyses (endpoints described in sections [7.4-7.6](#)):

As described in [Section 4](#), the follow-up period will not be included in the time at risk for efficacy endpoints. Therefore events later than the date of treatment discontinuation (if reason for discontinuation was completion) will not be counted.

For the primary endpoint and the key secondary endpoint of recurrent HHF, additionally there will be sensitivity analysis including all events up to individual trial completion including the FU period.

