7.5.2 Other Secondary endpoints

Other secondary endpoints are exploratory. No correction for multiple hypotheses testing will be made.

- *Composite renal endpoint: Time to first event of chronic dialysis or renal transplant or sustained* reduction of $\geq 40\%$ eGFR (CKD-EPI)_{cr} or*
 - *(for patients with eGFR (CKD-EPI)_{cr} ≥ 30 mL/min/1.73 m² at baseline): sustained eGFR < 15 mL/min/1.73m²*
 - *(for patients with eGFR (CKD-EPI)_{cr} < 30 mL/min/1.73 m² at baseline): sustained eGFR < 10 mL/min/1.73 m²*

*An eGFR (CDK-EPI)_{cr} reduction is considered sustained, if it is determined by two or more consecutive post-baseline central laboratory measurements separated by at least 30 days (first to last of the consecutive eGFR values). If there is no additional measurement ≥ 30 days after the eGFR reduction is observed and the patient dies within 60 days of this measurement, then the eGFR reduction is also considered sustained.

Chronic dialysis is regarded as chronic if the frequency of dialysis is twice or more per week for at least 90 days.

- *Time to first adjudicated HHF*
- *Time to adjudicated CV death*
- *Time to all-cause mortality*
- *Time to onset of DM in patients with baseline pre-DM*

All time-to-event endpoints will be reported in days.

The same model and data frame as used in the primary analysis of primary endpoint will be applied to all these time-to-event endpoints. If the endpoint does not include any cause of death, a CIF plot with all-cause mortality as competing risk will be displayed; otherwise, a CIF plot with causes of death not included in the endpoint as competing risk will be displayed. For all-cause mortality a Kaplan-Meier plot will be displayed.

For time to first HHF and time to CV death, the analysis will be repeated based on investigator defined events. In addition, the analysis of time to CV death will be repeated to include all events up to 7 days prior a reported SARS-CoV-2 infection (based on broad scope SARS-CoV-2 infections)

- *Change from baseline in clinical summary score (HF symptoms and physical limitations domains) of the Kansas City cardiomyopathy Questionnaire (KCCQ) at week 52*

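### The death clause for a sustained eGFR reduction, read literally, ignores a central value before day 30 that no longer meets the threshold

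*SAP*

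**What the plan says.** The main rule in SAP 6.6.2 (current version) requires "two or more consecutive post-baseline central laboratory measurements separated by at least 30 days (first to last of the consecutive eGFR values"). Because the values must be consecutive, a recovered value between two low ones breaks the run.

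A supplementary clause then covers deaths. If no further measurement exists 30 days or more after the reduction and "the patient dies within 60 days of this measurement, then the eGFR reduction is also considered sustained", confirmation is waived. These are its only two conditions. The same text stands under the composite renal endpoint in 7.5.2 and under the further endpoints in 7.6, and no other section adds a recovery check.

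Section 6.8.2 says that laboratory events, including sustained ones, "are determined by the date of the first measurement that fulfils this condition". An event created by the clause is therefore dated at the low value, not at death. On status, 7.5.2 says: "Other secondary endpoints are exploratory. No correction for multiple hypotheses testing will be made".

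**The concern.** The clause sits in the missing-data section, under a subheading about a confirming measurement that is missing. Its evident purpose is to avoid losing a renal event because death prevented the second sample. The wording reaches further. It also covers a patient who does have a later central value, if that value came before day 30 and no longer met the threshold. For that patient an imputation rule takes precedence over an observed result.

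At stake is the classification of such patients in the composite renal endpoint. That endpoint does not include death, and 7.5.2 displays it with all-cause mortality as the competing risk. The patient would be shown with a renal event rather than a competing death. Section 7.6 builds three further composites on the same definition.

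**Working it through.** The plan gives no figure to reproduce, so the check applies the rule as written to example patients.

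**Inputs.** Day 0 is the day of the low central value.
- Main rule (6.6.2): a run of consecutive low values with last day − first day ≥ 30.
- Death clause (6.6.2, 7.5.2, 7.6): no value on day 30 or later, and death day ≤ 60 (day 60 taken as included).
- Repaired clause: as above, and every central value after day 0 is also low.

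| Central values | Death | Main rule | Clause as written | Repaired clause |
|---|---|---|---|---|
| low d0 | d50 | no | event | event |
| low d0, low d14 | d50 | no | event | event |
| low d0, recovered d14 | d50 | no | event | no |
| low d0, recovered d29 | d60 | no | event | no |
| low d0, recovered d30 | d50 | no | no | no |
| low d0, recovered d14 | d61 | no | no | no |

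Rows 3 and 4 show the gap. Rows 4 and 5 show that one day's difference in the sampling date reverses the classification. The repair changes only rows 3 and 4 and keeps the cases the clause is evidently meant for.

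**Where could a value before day 30 come from?** Planned post-baseline days in Table 6.7: 1 are 29, 85, 225, 365, 533, 701, 869 and 1037. The gaps are 56, 140, 140, 168, 168, 168 and 168 days, so two scheduled on-treatment samples taken on their planned days cannot produce the pattern. Two routes remain.
1. An unscheduled central sample. The SAP does not mention rechecks after an acute fall. It does have a rule for choosing between two observations in one visit window, so it allows for extra values.
2. An end-of-treatment sample followed by the follow-up sample. The follow-up window opens at "Trt stop + 23 days" and closes at day 45. With the end-of-treatment sample taken on the stop day, follow-up on days 23 to 29 falls short of 30 days. For planned completers, 6.8.2 and 6.8.3 end efficacy risk time at treatment discontinuation, so only a low value dated on or before stop could count. The route is open mainly for patients who stopped early.

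**Effect by endpoint** (7.5.2, 7.6), where the death itself lies within the efficacy risk period:
- Composite renal endpoint alone: event status can change.
- Renal or all-cause mortality: the patient has an event anyway; only its date moves, by at most 60 days.
- Renal or CV death: CV deaths and deaths of undetermined cause (5.1) are events anyway; only a non-CV death can gain an event.
- Renal, CV death or HHF: as the previous line, and only if there was no adjudicated HHF.

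A planned completer who dies after the cut-off is an exception. That death is not counted, so a low value on or before stop could add an event in any of the four.

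**The case against.** The strongest reply is that context settles the meaning: the clause stands under missing data and was written for patients with no second sample, so a sensible programmer would not apply it against a recovered value. That intent is plausible, but the text tests only for values at day 30 or later, and two programmers could reasonably code it differently.

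A second reply is that one improved value shortly before death does not prove lasting renal recovery. That is fair. But the plan's own standard is a consecutive run of low values, and by that standard the run is broken.

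A third reply is that the pattern is very unlikely. Only central laboratory values count, so local hospital repeats do not create it, and the follow-up route needs several coincidences. This stands and limits the point.

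A reader might go further and infer that the clause regularly turns transient kidney injury into endpoints, that it inflates all three further composites, or that it biases the treatment comparison. The documents do not support this. They give no frequency, most affected deaths would be events in those composites anyway, and the rule is the same in both arms. Dating an event before the death is also not specific to this gap; it follows from any use of the clause together with 6.8.2.

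**Conclusion.** The gap in the definition is real: as written, the clause disregards a central value before day 30 that fails the threshold, contrary to the consecutive-values rule it supplements. Its reach is narrow. It bears mainly on event status in the exploratory composite renal endpoint and, to a lesser degree, on dates and a few non-CV deaths in the three further composites. The primary endpoint, recurrent HHF and eGFR slope do not use the rule.

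The number of patients cannot be derived from the SAP and may be zero. For scale only, assume equal arms of the roughly 5750 patients in 9.6 (5750 / 2 = 2875), a renal event in 3% to 6% of an arm (about 86 to 173 patients), and 0 to 5 affected patients, all in one arm. The share of that arm's renal events then runs from 0 to between 5 / 173 = 2.9% and 5 / 86 = 5.8%. Apart from the 5750, every input is an assumption, and the upper end is deliberately unfavourable. This is a desirable clarification and does not threaten the trial's conclusions.

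**What to change.** In 6.6.2, 7.5.2 and 7.6, add to the death clause that it applies only if every central eGFR value between the reduction and death, if any, also meets the relevant threshold. Patients with no later value, or with only low later values, stay classified as now. The cost is one phrase in three sections and one extra condition in the derivation program. It uses data already collected and changes no other analysis.
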